8.4.2 Clinical Laboratory

For the treatment-emergent laboratory assessments, the observed values and change from baseline values of the continuous hematology, chemistry, and coagulation results will be summarized in SI units at each scheduled visit by treatment groups.

The number and percentage of subjects with continuous hematology, chemistry and coagulation test values meeting at least 1 threshold analysis criterion event, during the TE period, will be summarized by treatment groups. The threshold analysis criteria are provided in [Appendix E](#).

Results of urinalysis and positive urine/serum pregnancy tests will be listed in individual subject data listings only. For positive serum pregnancy listing, subjects with serum HCG which are abnormally high will be selected.

In addition, a listing containing individual subject hematology, chemistry, and coagulation values will be provided. This listing will include data from both scheduled and unscheduled visits.

8.4.3 Electrocardiogram

For the treatment-emergent ECG measurements, a summary of observed values and change from baseline values will be provided at each scheduled visit by treatment groups, for the following ECG interval measurements (in msec): RR, PR, QT, and QT corrected for HR intervals (QTcF), QRS duration, and HR (beats per minute).

The number and percentage of subjects meeting at least 1 threshold analysis criterion during the TE period, will be summarized by treatment groups. The threshold analysis criteria are provided in [Appendix E](#).

In addition, a listing containing individual subject ECG values will be provided. This listing will include data from both scheduled and unscheduled visits.

8.4.4 Vital Signs

For the treatment-emergent vital signs measurements, the observed values and change from baseline values will be summarized by treatment groups. The following vital signs parameters will be summarized: systolic and diastolic blood pressure (mm Hg), body temperature (°C), pulse rate (beats per minute), respiratory rate (breaths per minute), Weight (kg), and Body Mass Index (kg/m²).

The number and percentage of subjects meeting at least 1 threshold analysis criterion during the TE period will be summarized by treatment groups. The threshold analysis criteria are provided in [Appendix E](#).

In addition, a listing containing individual subject vital signs values will be provided. This listing will include data from both scheduled and unscheduled visits.

8.4.5 Pulse Oximetry

[figure not shown]
For the treatment-emergent pulse oximetry measurements, a summary of observed values and change from baseline values will be provided at each scheduled visit, for the percent of oxygen saturation, by treatment groups.

The number and percentage of subjects with shift changes from baseline (normal/missing and low according to the reference range) to the lowest percent of oxygen saturation during the TE Period will be summarized by treatment groups.

In addition, a listing containing individual subject pulse oximetry values will be provided for each part. This listing will include data from both scheduled and unscheduled visits.

8.4.6 Physical Examination

PE findings will be presented as an individual subject data listing only.

9 INTERIM AND DMC ANALYSES

9.1 Interim Analysis

No interim analysis is planned.

9.2 DMC Analysis

The DMC's objectives and operational details are defined in a separate document (DMC Charter) which was finalized before the first subject was screened in the study. The DMC's planned safety reviews of study data are outlined in the DMC Charter and DMC Statistical Analysis Plan.

11 LIST OF APPENDICES

Appendix A: Analysis Visit Windows for Safety and Efficacy Assessments

Table 11-1 Analysis Visit Windows for Safety and Efficacy Assessments			
Assessment	Visit¹	Target Study Day	Analysis Visit Window (in study days)^{2,3,4}
Safety Analysis			
Serum Chemistry Hematology Weight/BMI	Day 1 (Baseline)	1	≤1 Pre-dose
	Day 15	15	[1, 22] Day 1 post dose
	Week 4	29	(22, 43]
	Week 8	57	(43, 71]
	Week 12	85	(71, 99]
	Safety Follow-up	Not applicable	Use nominal visit
Coagulation	Day 1 (Baseline; before dosing)	1	Use nominal visit for all post-baseline visits
	Week 12	Not applicable	
	Safety Follow-up	Not applicable	
Vital Signs Pulse Oximetry	Day 1 (Baseline)	1	≤1 Pre-dose
	Day 15	15	[1, 22] Day 1 post dose
	Week 4	29	(22, 43]
	Week 8	57	(43, 71]
	Week 12	85	(71, Week 12 visit date ⁵)
	Washout Visit	Not applicable	Use nominal visit
	Safety Follow-up	Not applicable	Use nominal visit
Standard 12-Lead ECG	Day 1 (Baseline; before dosing)	1	Use nominal visit for all post-baseline visits
	Week 4	Not applicable	
	Safety Follow-up	Not applicable	
Efficacy and Pharmacodynamic Analysis			
Spirometry ⁶ Sweat Chloride ⁶	Day 1 (Baseline)	1	≤1 Pre-dose
	Day 15	15	(1, 22]
	Week 4	29	(22, 43]
	Week 8	57	(43, 71]
	Week 12	85	(71, Week 12 visit date ⁵)
	Washout Visit	Not applicable	Use nominal visit
	Safety Follow-up	Not applicable	Use nominal visit
Notes:			
1 Visit name for analysis purpose is used to report data in tables and figures.			
2 The analysis visit windows will be applied using the following rules for both scheduled and unscheduled visits:			
a. If no numerical measurement is available within a visit window, the measurement will be considered missing for the visit.			
b. If there is more than 1 numerical measurement available within the same visit window, use the following rules:			
i. The measurement closest to the target day will be used; or			
ii. If there are multiple measurements within the same distance from the target day, the latest measurement will be used.			
3 For measurements collected on the date of first dose of study drug, if it cannot be determined whether the measurements are before or after the first dose:			
a. Scheduled measurement will be treated as pre-dose observation.			
b. Unscheduled measurement will be treated as post-dose observation.			

Table 11-1 Analysis Visit Windows for Safety and Efficacy Assessments			
Assessment	Visit¹	Target Study Day	Analysis Visit Window (in study days)^{2,3,4}

4. When the ETT visit replaces the Safety Follow-up visit, it will be mapped to the Safety Follow-up visit. Other ETT visits will be mapped according to the analysis visit windowing rule for safety analysis.
 
5. If the week 12 visit is not available, then no assessment will be mapped to the Week 12 analysis visit.
 
6. Except for safety follow-up visit (or ETT replacing safety follow-up visit) and washout visit (given that Week 12 visit is completed), spirometry and sweat chloride assessments after last dose date will not be mapped to analysis visits.
 
Derived Variables
 
1. Age (in years) at first dose date and nominal visit (for demographics, listing and the calculation of [percent] predicted spirometry variable)
 
Obtain age at informed consent (in days) in “yy, mm” format (e.g., 24 years, 6 months) from Vital Signs page at the Screening Visit, and add 0.5 month to convert to days.
 
Obtain informed consent date.
 
Then age (in years) at first dose date or nominal visit = [(first dose date or nominal visit date – informed consent date) in days + age at informed consent (in days)]/365.25.
 
2. Missing first dose date or last dose date
 
If the first dose date is missing, use Day 1 visit date to impute.
 
If the last dose date is missing or partial date is reported, the last dose date will be imputed based on, in descending order priority, the Early Treatment Termination (ETT) visit date, last visit date before the Safety Follow-up, or the last study drug administration date from EX SDTM domain, as appropriate. The imputation algorithm will ensure the imputed last dose date does not exceed the study participation end date.
 
3. Sweat Chloride:
 
Non-missing sweat chloride concentrations from the left arm and right arm with the assessment end date/time for a given arm up to 30 minutes after first dose time in treatment period will be considered for baseline.
 
4. Electrocardiogram:
 
Baseline is defined as the most recent pretreatment measurement before the first dose of study drug in the Treatment Period (or the average of triplicate measurements, if the most recent non-missing measurement is obtained in triplicate at screening). If multiple ECG measurements are obtained on the same visit during the TE period,
 
 ○ For summary purpose, the nominal scheduled ECG will be used as the ECG value for the visit; ○ For threshold analysis purpose, all reported ECG values will be used. 			

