^o Blood samples will be collected for PK analysis of VX-561 and metabolites or IVA and metabolites. The sample collected at Screening will be collected without regard to time of IVA dosing. On Day 1, samples will be collected before dosing (0 hours) and at 4 hours after dosing (relative to the morning dose). At Day 15, Week 4, Week 8, and Week 12, a predose sample will be collected before the morning dose. In a subset of subjects (up to approximately 20 subjects), additional samples will be collected at the Week 4 visit at 1, 2, 4, and 6 hours after dosing (relative to the morning dose). At the Washout Visit, a single sample will be collected prior to resumption of IVA. A single sample will be collected at the Safety Follow-up Visit for analysis of IVA for those subjects who resume IVA therapy. Acceptable PK sampling windows are provided in Table 11-1. At the ETT Visit, a single blood sample for PK analysis will be collected.

^p Study drug will be administered orally twice daily (Section 9.6). The last dose of study drug will be the morning dose on the Week 12 Visit. Subjects may resume their prior IVA therapy after the Washout Visit.

^q All medications taken from 28 days before the Screening Period through the end of the study will be recorded (Section 9.5).

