7 STUDY ENDPOINTS

7.1 Primary Endpoint

- Absolute change in ppFEV₁ from baseline at Week 12

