5 STUDY ENDPOINTS

5.1 Primary Endpoint

- Absolute change in percent predicted forced expiratory volume in 1 second (ppFEV₁) from baseline at Week 12

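### SAP Table 11-1 writes the Week 12 window as open at the Week 12 visit date, so read literally it leaves out the scheduled Week 12 value; a minor notation error in an operative rule

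*SAP*

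**What the plan says.** The primary endpoint is the "Absolute change in ppFEV₁ from baseline at Week 12" (Protocol 7.1; SAP 5.1 agrees). SAP Appendix A, Table 11-1 decides which measurement counts as the Week 12 value.

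- **Week 12 window.** In the Spirometry/Sweat Chloride row and the Vital Signs/Pulse Oximetry row the limits are "71, Week 12 visit date ⁵", with a round bracket at each end. The raised 5 points to note 5.
- **Other windows.** Every numeric window after baseline has a closed upper limit: 22], 43], 71] and, for Week 12 chemistry, hematology and weight, 99].
- **Empty window (note 2a).** "If no numerical measurement is available within a visit window, the measurement will be considered missing for the visit".
- **Several values (note 2b).** "The measurement closest to the target day will be used"; the Week 12 target is Day 85.
- **Note 5.** "If the week 12 visit is not available, then no assessment will be mapped to the Week 12 analysis visit".
- **Note 6.** Apart from the washout and safety follow-up visits, "spirometry and sweat chloride assessments after last dose date will not be mapped to analysis visits".

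The schedule of assessments (Protocol Section 3) adds: "The last dose of study drug will be the morning dose on the Week 12 Visit". SAP 8.1 leaves missing data unimputed unless stated otherwise, and SAP 8.3.1.3 plans no sensitivity analysis.

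**The concern.** In standard interval notation a round bracket excludes the limit and a square one includes it. Table 11-1 appears to use the difference on purpose: the Day 15 window starts at [1 in the safety rows and at (1 in the efficacy row. On that convention the two Week 12 rows exclude the visit date, which is the day on which the scheduled Week 12 measurement is taken.

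These rows select the Week 12 ppFEV₁ and sweat chloride values for the primary analysis and the secondary PD analysis. The washout and safety follow-up rows fall back on the nominal visit, but the Week 12 rows do not, and nowhere does the SAP say in words that the upper limit is inclusive. Code written strictly from the table would set a completer's Week 12 value to missing, or replace it with something measured earlier.

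**Working it through.** **1. The plan's own precision figures.** Inputs from SAP 6.2 and Protocol 12.1: SD 7, dropout 10%, 22 to 28 per VX-561 arm, 11 to 14 in the IVA arm. Evaluable number m = 0.9n rounded down; half-width = t(0.975, m−1) × 7/√m.

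| n | m | Half-width | Stated |
|---|---|---|---|
| 22 | 19 | 3.37 | 3.4 |
| 28 | 25 | 2.89 | 2.9 |
| 11 | 9 | 5.38 | 5.4 |
| 14 | 12 | 4.448 | 4.4 |

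All four reproduce. None depends on Table 11-1; they serve here to fix the number of expected completers.

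**2. Is the visit in its own window?** The schedule allows Week 12 ± 5 days, so around target Day 85 the visit day V runs from 80 to 90, which is 11 possible days.

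- As written, (71, V): requires 71 < V < V. False on all 11 days.
- Closed, (71, V]: requires 71 < V ≤ V. True on all 11 days.
- The laboratory window, (71, 99]: true on all 11 days.

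**3. What the literal window admits.** Days 72 to V−1: Days 72 to 79 if V = 80, and Days 72 to 89 if V = 90. Two kinds of value could fall there, because note 2 covers scheduled and unscheduled visits alike: an unscheduled measurement, or a late Week 8 visit. The latter would have to be very late. Week 8 has target Day 57 and a ± 5 day allowance, so its last permitted day is 62, and Day 72 is 10 days beyond that. If neither exists, note 2a makes Week 12 missing.

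**4. What the other text implies.** Note 5 makes the Week 12 visit a precondition for any Week 12 mapping, which would be pointless if that visit's own measurement were then dropped. Note 6 bars spirometry and sweat chloride only after the last dose date. For a completer that date is the Week 12 visit itself, so a measurement on that day is not barred. The endpoint and the MMRM in SAP 8.3.1.2 both need a Week 12 value. Note 6 does not cover vital signs and oximetry; for that row the inference rests on note 5 and the identical wording.

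**5. How many subjects literal coding would reach.** Lower planned sizes: 19 + 19 + 9 = 47. Upper planned sizes: 25 + 25 + 12 = 62.

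**6. Does closing the limit let in washout data?** The washout visit is 4 ± 1 days after the Week 12 visit, so V+3 to V+5. All of these lie beyond V and stay out. By contrast, borrowing (71, 99] from the laboratory row would be wrong here: over V = 80 to 90 the washout visit falls on Days 83 to 95, all inside that window.

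**The case against.** The case against has four parts.

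- **The character itself.** The point rests on one character directly after a superscript, in text extracted from PDF. The two rows carry the same string, so the repeat is not independent confirmation, and the numeric cells that kept a square bracket have no superscript before it. This stands as a caveat: the bracket must be checked in the source.
- **The form of the cell.** The upper limit is a visit date in words, so the last bracket might simply match the opening one. That is possible, but the rest of the table gives the closing bracket a meaning and nothing exempts these two rows.
- **The intent.** Notes 5 and 6 and the endpoint show that the visit was meant to count. This stands, and it is why the point is minor.
- **The consequence.** Literal coding would leave the Week 12 column nearly empty and the primary estimate essentially inestimable. That is a conspicuous failure, not a hidden bias. This also stands.

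Some stronger readings are tempting, and the documents do not support them. A reader might infer that note 5 contradicts the table; it only deals with an absent visit, and it clarifies the cell. A reader might infer that values prompted by illness would replace the scheduled ones; nothing in either document describes illness-triggered spirometry, and a late Week 8 visit could map as well. A reader might take 62 as the number affected; it is only the upper end of a range that counts completers, and it does not forecast any effect on the estimate.

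**Conclusion.** The window is wrong as written, provided the source PDF shows the same bracket. Applied literally, it excludes the scheduled Week 12 measurement on every permitted visit day, for about 47 to 62 expected completers. That range assumes the SAP's planned arm sizes, 10% dropout and rounding down within each arm.

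A reader might conclude that the trial discards its own primary endpoint. The documents do not bear that out: the intended rule can be recovered from the notes, a programmer would very probably apply it, and a departure would show at the first run of the outputs. No sample size, precision figure or design element is affected. The error deserves correction because it sits in the rule that picks the primary endpoint value, and that rule should not need to be inferred.

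**What to change.** Check the closing bracket in the source PDF of SAP Appendix A, Table 11-1. If it is round there too, write (71, Week 12 visit date] in both the Spirometry/Sweat Chloride row and the Vital Signs/Pulse Oximetry row, keeping the reference to note 5. Do not substitute the laboratory window, since it would take in the washout visit.

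The cost is two characters, made before the SAP is finalized ahead of data lock and unblinding. If analysis programs already exist, confirm that they include the visit date.

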3 SCHEDULE OF ASSESSMENTS

The schedule of assessments is provided in [Table 3-1](#).

Table 3-1 Study VX18-561-101: Screening Visit, Treatment Period, Washout Visit, and Safety Follow-up Visit

Event/Assessment ^a	Screening Visit ^b	Treatment Period					Washout Visit	ETT Visit ^c	Safety Follow-up 28 (± 7) Days After Last Dose of Study Drug
	Day -28 to Day -1	Day 1	Day 15 (± 3 day)	Week 4 (± 5 days)	Week 8 (± 5 days)	Week 12 (± 5 days)	4 (± 1) Days After Week 12 Visit		
Outpatient visits	X	X	X	X	X	X	X	X	X
Randomization ^d		X							
Demographics	X								
Medical history	X								
Weight ^e	X	X	X	X	X	X		X	X
Height ^e	X								
Vital signs ^f	X	X	X	X	X	X	X	X	X
Pulse oximetry ^f	X	X	X	X	X	X	X	X	X
Physical examination ^g	Complete	Abbrev.		Abbrev.	Abbrev.	Abbrev.		Abbrev.	Abbrev.
Standard 12-lead ECG ^h	X	X		X				X	X
Sweat chloride ^{i,j}	X	X	X	X	X	X	X	X	X

^a All assessments will be performed before dosing, unless noted otherwise. Assessments may be performed in any order when more than 1 assessment is required at a particular time point. Assessments that are collected before and after dosing will only be collected once if study drug is not administered on the day of the visit (i.e., premature discontinuation of study drug treatment).

^b All screening results must be reviewed before randomization, unless noted otherwise.

^c If the subject prematurely discontinues study drug, an ETT Visit should be scheduled as soon as possible after the decision to terminate study drug treatment. Additional PK samples and safety assessments may also be performed at the discretion of the investigator. See Section 9.1.5 for additional details.

^d Randomization may occur on the previous day (Day -1) after eligibility has been confirmed.

^e Weight and height will be measured with shoes off.

^f Vital signs and pulse oximetry will be collected after the subject has been at rest for at least 5 minutes.

^g Complete and abbreviated PEs are described in Section 11.5.3.

^h Standard 12-lead ECGs will be performed in the supine position after the subject has been at rest for at least 5 minutes. See Section 8.2 for information about the ECG assessment for study eligibility.

ⁱ Sweat chloride assessments should be performed at approximately the same time at every visit. See Section 8.1 for information about the sweat chloride assessment for study eligibility.

^j The pre-dose assessment on Day 1 may be performed on the previous day (Day -1) if randomization has occurred.

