9.1.5 Early Termination of Treatment OR Early Discontinuation

If a subject prematurely discontinues study treatment, an Early Termination of Treatment (ETT) Visit should be scheduled as soon as possible after the subject decides to terminate study treatment. Subjects who prematurely discontinue treatment will also be required to complete the Safety Follow-up Visit, approximately 28 (± 7) days after their last dose of study drug. The assessments performed at the Safety Follow-up Visit are listed in [Table 3-1](#).

Subjects who discontinue from study drug dosing for any reason (except withdrawal of consent) will have a final PK blood sample drawn as soon as possible after the decision to discontinue study drug is made. Additional safety assessments may also be performed at the discretion of the investigator, including possible consultation with a specialist consultant. The Vertex medical monitor will be informed about these additional assessments, and any additional data collected (e.g., as the result of an outside consultation) will be considered part of the study record to provide the most complete safety profile of the study drug.

If the ETT Visit occurs 3 weeks or later following the last dose of study drug, then the ETT Visit will replace the Safety Follow-up Visit, and a separate Safety Follow-up Visit will not be required.

If a subject withdraws consent for the study, no further assessments will be performed, and no additional data should be collected. Vertex may retain and continue to use any data and samples collected before such withdrawal of consent.

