8.3.1.2 Primary Analysis

The primary efficacy endpoint is the absolute change in ppFEV₁ from baseline at Week 12. Per Protocol Version 2.0, the lower dose VX-561 arms (VX-561 25 mg qd and 50 mg qd) were discontinued. Most of the 17 subjects randomized to lower dose arms (VX-561 25 mg qd and 50

mg qd) did not complete study treatment. Due to the large proportion of missing assessments of lower dose arms, they are not included in MMRM analysis. The primary analysis (described below) is based on the within group mean of absolute change from baseline for VX-561 150 mg qd, VX-561 250 mg qd, and IVA 150 mg q12h treatment arms.

The primary analysis will be based on a mixed effects model for repeated measures (MMRM) using restricted maximum likelihood. The model will include the absolute change from baseline in ppFEV₁ at Day 15, Week 4, Week 8, and Week 12 from the current treatment arms (VX-561 150 mg qd, VX-561 250 mg qd, and IVA 150 mg q12h) as the dependent variable; treatment group, visit, and treatment by visit as fixed effects; with continuous baseline ppFEV₁ as covariates; and an unstructured covariance structure for the within-subject errors. If the model estimation does not converge, a compound symmetry covariance structure will be used. The efficacy data from the discontinued arms (VX-561 25 mg qd and VX-561 50 mg qd) will not be included in the model.

The primary results obtained from the model will be the within-group treatment effect estimate at Week 12 for each treatment arm. The adjusted mean with a 2-sided 95% CI will be presented in a table.

In addition, the adjusted mean and 95% CI of the treatment effect difference between each VX-561 arm and the IVA arm obtained from the MMRM model will be provided.

The ppFEV₁ values and absolute change from baseline values will be summarized descriptively (n, mean, SD, median, minimum and maximum) at each scheduled visit by treatment groups (in one table including IVA, VX-561 25 mg qd, VX-561 50 mg qd, VX-561 150 mg qd, VX-561 250 mg qd).

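### SAP Appendix A places off-drug early-termination labs and vital signs in treatment-period visit rows of the by-visit safety tables, and gives other early-termination values, including ECG and coagulation, no row

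*SAP*

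**What the plan says.** Protocol 9.1.5 lets an ETT visit stand in for Safety Follow-up only when it is late: "If the ETT Visit occurs 3 weeks or later following the last dose of study drug". SAP Appendix A (Table 11-1, note 4) follows this: "When the ETT visit replaces the Safety Follow-up visit, it will be mapped to the Safety Follow-up visit". For the rest: "Other ETT visits will be mapped according to the analysis visit windowing rule for safety analysis".

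Note 6 adds, with exceptions for the Safety Follow-up and Washout visits, that "spirometry and sweat chloride assessments after last dose date will not be mapped to analysis visits". Safety data have no matching rule.

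The post-baseline rows of Table 11-1 are:

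| Assessment | Rows and windows (study days) |
|---|---|
| Chemistry, hematology, weight/BMI | Day 15: to 22; Week 4: 23–43; Week 8: 44–71; Week 12: 72–99; Safety Follow-up: nominal |
| Vital signs, oximetry | Same through Week 8; Week 12: from 72 to the Week 12 visit date; Washout and Safety Follow-up: nominal |
| Coagulation | Week 12 and Safety Follow-up, nominal only |
| ECG | Week 4 and Safety Follow-up, nominal only |

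For coagulation and ECG the instruction is "Use nominal visit for all post-baseline visits". Note 5, marked on the vital-sign/oximetry and efficacy Week 12 windows, reads: "If the week 12 visit is not available, then no assessment will be mapped to the Week 12 analysis visit". Protocol Table 3-1 marks the ETT column in both the "Standard 12-lead ECG" row and the coagulation row.

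SAP 8.4.2 to 8.4.5 describe these summaries as treatment-emergent. Under SAP 8.1 that period runs to 28 days after the last dose, or to the end of participation if earlier.

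**The concern.** A row labelled Week 8 will be read as a description of subjects about eight weeks into dosing. Under note 4 it can also hold values from subjects who stopped well before that visit, with nothing to separate the two. The SAP took care to prevent this for spirometry and sweat chloride, but not for safety.

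ECG and coagulation have the opposite problem. Note 4 refers ETT visits to a windowing rule that these two assessments do not have. Coagulation is scheduled after Day 1 only at Week 12, ETT and Safety Follow-up. For a subject who stops early, the ETT sample is therefore the scheduled result nearest to dosing. For a subject who stops before Week 4, the ETT ECG is the first scheduled ECG after dosing began. Neither has a by-visit row unless the ETT visit replaces Safety Follow-up.

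The protocol synopsis says safety in all arms, including the two discontinued ones, is analysed to support dose selection. Early stopping is concentrated in those two arms: "Most of the 17 subjects randomized to lower dose arms" did not complete treatment (SAP 8.3.1.2).

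**Working it through.** The plan gives no figure of its own here, so the check applies its rules directly.

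**1. Largest off-drug lag.** Three weeks is 21 days, and from that lag the ETT visit is mapped to Safety Follow-up. The study-day windows therefore receive lags of 0 to 20 days. Table 3-1 and Protocol 9.1.5 ask for the ETT visit without delay, so 20 is a ceiling and not a typical value.

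**2. Where one ETT visit goes** (subject with no Week 12 visit):

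| Last dose | ETT | Lag | Chemistry, hematology, weight | Vital signs, oximetry | ECG, coagulation |
|---|---|---|---|---|---|
| Day 28 | Day 44 | 44 − 28 = 16 | Week 8 | Week 8 | no row |
| Day 60 | Day 80 | 80 − 60 = 20 | Week 12 | no row (note 5) | no row |

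In the second line a single visit is handled in three ways. Note 5 carries no marker on the laboratory window, but its text speaks of assessments in general. If a programmer applied it to laboratory values too, ETT labs after Day 71 would have no row.

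**3. Reach of the rule.** Take last-dose Days 1 to 84 and lags 1 to 20: 84 × 20 = 1,680 combinations. Assume no Week 12 visit, and scheduled visits attended on the target day while dosed.

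| | Falls in a Day 15–Week 12 window | Loses to a scheduled value | Supplies the table value | Rows where the lag can reach 20 days |
|---|---|---|---|---|
| Labs, weight | 1,665 (99%) | 238 | 1,665 − 238 = 1,427 (85%) | Day 15, Weeks 4, 8, 12 |
| Vital signs, oximetry | 1,210 (72%) | 238 | 1,210 − 238 = 972 (58%) | Day 15, Weeks 4, 8 |

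The combinations are weighted equally, which is an assumption. The percentages show how far the rule reaches and are not expected frequencies.

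**4. Completers.** Inputs:
- The last dose is the morning dose at the Week 12 visit (Table 3-1, footnote p).
- The visit window is Day 85 ± 5, that is Days 80 to 90, or 11 days.
- A new ALT or AST above 3 × ULN, or bilirubin above 2 × ULN, calls for a confirmatory test within 48 to 72 hours (Protocol 9.8).
- Unscheduled values enter the windows (SAP 8.1). The value nearest the target is used, and equal distances go to the later one (note 2b).

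For a visit on day V and a retest k days later, the retest supplies the table value when |V + k − 85| ≤ |V − 85|.

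| V | Distance, visit | Distance, k = 2 | Distance, k = 3 | Retest used? |
|---|---|---|---|---|
| 80 | 5 | 3 | 2 | both |
| 81 | 4 | 2 | 1 | both |
| 82 | 3 | 1 | 0 | both |
| 83 | 2 | 0 | 1 | both |
| 84 | 1 | 1 (tie) | 2 | k = 2 only |
| 85–90 | 0–5 | 2–7 | 3–8 | neither |

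So 5 of the 11 allowed visit days are affected at 48 hours and 4 of 11 at 72 hours.

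**5. What is untouched.** Threshold analyses count values across the treatment-emergent period (SAP 8.4.2 to 8.4.4), and Appendix A uses every reported ECG for them. Listings hold the individual values. Note 6 protects the ppFEV1 and sweat chloride analyses.

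**The case against.** The best defence is that note 4 is a stated convention. The tables are described as treatment-emergent, that period extends 28 days beyond the last dose, and every lag of 0 to 20 days lies inside it. This stands against any claim that off-drug values are reported as on-treatment: a reader might infer that from the row labels, but the SAP does not say it. It does not remove the mixing of dosed and undosed values under one label.

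The wider laboratory window also has a plausible design reason. The windows that close at the Week 12 visit belong to assessments repeated at the Washout Visit, which has its own row. Chemistry, hematology and weight are not scheduled there, so 85 ± 14 days is an ordinary symmetric window. The difference is therefore not an error in itself; its side effect is to let an off-drug retest in.

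The retest effect is narrow. It needs a qualifying elevation, and the 48 to 72 hours run from the finding, which may come later than the blood draw. Laboratory turnaround is not stated. If draw and retest are 4, 5 or 7 days apart, the same inequality gives 4, 3 or 2 affected visit days of 11.

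Finally, safety is descriptive only, and SAP Section 3 already urges caution because most low-dose subjects did not complete treatment. This limits the severity and is accepted.

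**Conclusion.** The point holds as a gap in visit mapping, limited to by-visit descriptive safety summaries. Off-drug ETT labs and weight, up to 20 days after the last dose, can enter the Day 15 to Week 12 rows. Off-drug vital signs and oximetry can enter the Day 15 to Week 8 rows. ETT vital signs and oximetry after Day 71, and non-replacing ETT ECG and coagulation values, have no row. This rests on a literal reading of notes 4 to 6, with note 5 applied only where it is marked.

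Two further inferences are not supported. First, non-completion in the low-dose arms and the 10% dropout assumption might be turned into numbers of affected subjects. The documents do not say how many attended an ETT visit or how long after the last dose, and subjects who withdraw consent have no further assessments. Second, the ECG and coagulation values might be thought lost. They stay in the threshold analyses and listings, and an ETT visit at 21 days or later goes to Safety Follow-up.

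Severity is minor; this is a cheap improvement.

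**What to change.** Make two changes to Table 11-1 together:

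1. Add a separate ETT analysis visit, showing days since last dose, for chemistry, hematology, weight, coagulation, ECG, vital signs and oximetry. Reword note 4 so that non-replacing ETT visits go to that row instead of the study-day windows.
2. End the Week 12 window for chemistry, hematology and weight at the Week 12 visit date, inclusive.

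Neither half-measure works. Extending note 6 to safety data would still leave ETT ECG and coagulation values without a row. Capping the laboratory window without an ETT row would do the same to ETT labs after Day 71. Keep all values in the treatment-emergent threshold tables and listings.

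The cost is SAP text and a small change to the visit-mapping program; no new data are needed. The late by-visit cells will hold fewer values, mainly in the discontinued low-dose arms.
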